#### **6.2 Secondary Objectives:**

- Assess the utility of hepcidin and CRP in predicting response to FCM
- Assess the effect of FCM on the need for blood transfusions
- Assess the effect of FCM on the need for ESAs

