#### 8.3 Subject Withdrawal

Patients are free to withdraw from the study at any time without prejudice or loss of benefits to which they are otherwise entitled. The investigator may remove a patient from the study if, at his discretion, the participation is seen to jeopardize the patient safety or for administrative or behavioral reasons. Neither the investigator nor the study supporting staff will try to coerce patients to continue participating in the study against their will. The withdrawal case with reasons will be documented. Withdrawn subjects will be replaced to have a complete set of 50 analyzable subjects in each strata.

Additionally, patient will be dropped out and will be considered treatment failure if

- 1 .Receive ESA or blood transfusion for medical reasons not related to the study
- 2. if they Develop a grade IV toxicity of any kind in the week between the initial and the remaining dose that is possibly related to study drug.

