#### 10.3 Follow-up

- Hemoglobin assessments will be carried out every 3 weeks in line with the chemotherapy protocol visits and at week 12.
- Laboratory monitoring of ALT, AST, LDH, Alk-phosphatase, GGT and phosphorous will be done at week-3
- Ferritin level will be repeated at week-12
- A total of four follow-up visits are required for the study: weeks 3, 6, 9 and 12.

Figure 1 Study Scheme

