#### **11.2 Management of Adverse Events**

Standard medical care will be followed in managing adverse events reported during the study in compliance with in house policies and procedures. The PI may ask for additional tests to be done if the adverse event warrants an investigation. The patient will be treated free of charge for all study related events. If the patient is to be discontinued from the study because of the AE he/she will be followed up until the AE abates or returns to baseline.

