#### 13.3 Safety Analysis

Rate and incidence of adverse events will be analyzed and reported. Number of patients requiring ESA or transfusions will be reported using percentages and counts. PRT-INM-0615/09 V06

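### Section 8.3 drops patients from the study when they receive ESA or a transfusion, so new adverse events in these dosed patients are no longer sought, and no safety population is defined

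*Protocol*

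**What the plan says.** Protocol section 8.3 first covers voluntary and investigator-led withdrawal and says "Withdrawn subjects will be replaced to have a complete set of 50 analyzable subjects in each strata". It then adds a separate rule: "Additionally, patient will be dropped out and will be considered treatment failure if" they "Receive ESA or blood transfusion for medical reasons not related to the study". Grade IV toxicity between the two infusions is the other trigger.

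The search for harm after dosing is tied to study visits. Section 10.3 states "A total of four follow-up visits are required for the study: weeks 3, 6, 9 and 12", and Table 1 places adverse-event monitoring at those four visits. Section 10.3 also states "Laboratory monitoring of ALT, AST, LDH, Alk-phosphatase, GGT and phosphorous will be done at week-3". Ferritin is repeated only at week 12.

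Three passages touch on patients who leave:
- Section 11.2: "If the patient is to be discontinued from the study because of the AE he/she will be followed up until the AE abates". A return to the baseline state is given as the alternative end point.
- Section 11.4 follows all patients until an adverse event resolves, by telephone or outside the scheduled visits if needed.
- Section 16.7 promises appropriate follow-up measures before a file is closed, without saying what they are or how long they last.

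For analysis, section 13.3 and the Safety Analysis part of the SAP plan the rate and incidence of adverse events, and "Number of patients requiring ESA or transfusions will be reported using percentages and counts". Neither defines a safety population, a denominator or an observation period. Section 6.3.2 has one endpoint combining transfusion and ESA. Section 6.2 lists transfusion need and, separately, "Assess the effect of FCM on the need for ESAs".

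**The concern.** Classing a patient as a failure is enough to settle the response endpoint. Removing the patient from the study adds nothing to that endpoint, but it stops the visits at which new adverse events are looked for. The patients affected are selected by an outcome, not at random, and they have received an investigational infusion.

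At stake is the adverse-event summary. If all dosed patients form the denominator, each missed visit can only lower the number of patients seen to have an event. If the summary is a rate per unit of observation time, the bias depends on whether risk after rescue differs from risk before it, and the plan would hold no data to show that. With no stated population, it is also open whether these patients stay in the denominator at all.

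A smaller matter concerns section 6.2. A patient dropped at a first transfusion can no longer be seen to need ESA, or the reverse, so the separate tallies can each miss later use of the other treatment.

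**Working it through.** The plan states no figure on this point that could be reproduced. The check is a comparison of passages, followed by a calculation of how much follow-up is at risk.

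**Step 1: does any passage keep a dropped patient under observation for new events?**
- Section 11.2 applies when the reason for discontinuation is an adverse event. ESA or transfusion is a different reason.
- Section 11.4 applies to everyone, but it follows an event already recorded. It does not look for the next one.
- Section 16.7 is generic and gives no content or duration.
- No passage says that a patient dropped under 8.3 keeps the visits at weeks 3 to 12.

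**Step 2: inputs.**
- Pilot (section 5.2): 5 patients transfused, given as 20.0%, so 5 / 0.20 = 25 patients. The exact (Clopper-Pearson) 95% CI for 5/25 is 6.8% to 40.7%.
- Planned sample (section 13.1): 2 × 50 = 100 patients.
- Follow-up: 12 weeks, 4 visits each, so 400 scheduled adverse-event visits.
- Assumed: the pilot rate q = 20% applies here and every such transfusion triggers the drop, giving 20 dropped patients (7 to 41 across the CI). The documents give no distribution for the week of rescue t, so several values are shown.

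**Step 3: follow-up lost.**
Share of visits lost = q × (visits after t) / 4. Share of person-time lost = q × (12 − t) / 12.

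| Week of rescue | Visits lost per dropped patient | Share of 400 visits | Share of person-time |
|---|---|---|---|
| 2 | 4 | 20% | 16.7% |
| 3 (visit done) | 3 | 15% | 15.0% |
| 6 (visit done) | 2 | 10% | 10.0% |
| 9 (visit done) | 1 | 5% | 5.0% |
| uniform over weeks 0 to 12 | 2.5 on average | 12.5% | 10.0% |

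Uniform case: visit v is lost with probability v/12, and (3 + 6 + 9 + 12) / 12 = 2.5 visits; 20% × 2.5 / 4 = 12.5%. With q at the CI limits, the same formula gives 6.8% × 0.625 = 4.3% and 40.7% × 0.625 = 25.4%.

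**Step 4: week-3 chemistry.**
This is one draw, lost only if t < 3. Under uniform timing, 20 × 3/12 = 5 of 100 patients miss it. The extremes are 0 (all rescues at or after that visit) and 20 (all before it).

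**Step 5: transfusion and ESA counts.**
For the combined endpoint, the event that ends follow-up is the event counted, so a patient's own rescue removes 0 patients. For separate tallies, a later switch to the other treatment is missed. The documents give no switch rate; if 10% to 50% of 20 rescued patients switched, 2 to 10 would be missed from the tally of the second treatment.

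**The case against.** Several points on the other side stand.

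- **Counts of rescue.** A reader might infer that the transfusion and ESA figures as a whole come from truncated follow-up. Sections 6.3.2 and 13.3 count patients needing transfusion or ESA, and a rescued patient is already counted. Only the separate objectives in 6.2, and repeat use, can be affected.
- **Safety labs.** A reader might infer that the drop ends all laboratory safety monitoring. The liver and phosphate tests are a single week-3 draw, and anyone rescued at or after that visit has had it.
- **Who is dropped.** It is tempting to call these the sickest patients, fully exposed to FCM. The documents do not say they are the sickest. Under section 10.2, doses above 1000 mg are split a week apart, so a patient dropped between infusions has not had the whole dose.
- **The trigger.** Section 8.3 limits it to medical reasons not related to the study. If that excludes transfusion for the anemia under study, fewer patients are affected than the pilot rate implies. The text does not settle this.
- **Replacement.** The replacement sentence speaks of withdrawn subjects and comes before the treatment-failure rule. Patients classed as failures have an outcome and may count among the 50 analyzable. The documents do not clearly say that they are replaced.
- **Duration of effect.** Section 16.1 argues that a dose is expected to last only 72 hours and that reactions are transient, so late drops may hide few FCM-related events. That is an argument about likely yield; the plan still schedules adverse-event checks to week 12.

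It is also an inference that being dropped cancels the later visits, since 8.3 does not say so outright. It is the natural reading, and no passage says otherwise. Sections 11.4 and 16.7 show that patients are not simply abandoned, but neither provides a search for new events.

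**Conclusion.** The concern holds for adverse-event ascertainment and for the missing safety population. As written, 8.3 attaches leaving the study to an event for which failure status alone would do, and scheduled detection of new harm stops with it.

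At the pilot's 20% rate, 5% to 20% of scheduled adverse-event visits are at risk, 12.5% under uniform timing, and about 5 of 100 patients would miss the week-3 chemistry under uniform timing. These figures assume that the pilot rate carries over, although the pilot used a different iron product in non-iron-deficient patients only. They also assume that every transfusion triggers the drop and that being dropped ends the visits. They measure lost observation, not lost events; the size of any bias in adverse-event incidence cannot be derived from the documents.

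The concern does not extend to the combined transfusion-or-ESA endpoint, and it does not establish that failures are replaced. The change should be made because it is cheap and the loss falls on an outcome-selected group.

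**What to change.** In section 8.3, separate treatment failure from leaving the study. A patient given ESA or a transfusion under this rule counts as a failure for response but stays in scheduled data collection to week 12 unless consent is withdrawn: adverse events, week-3 labs, week-12 ferritin, and any later ESA or transfusion. In the same edit, state what the qualifier about reasons not related to the study covers, and whether patients classed as failures are replaced.

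In section 13.3 and the SAP, define the safety population as all patients who received any FCM, including any who are replaced. Use it as the denominator for adverse events, ESA and transfusion, and give the observation time behind the adverse-event rates. Report ESA and transfusion separately as well as combined.

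The cost is wording in two documents and slightly more visit documentation; section 10.3 already aligns the hemoglobin assessments with chemotherapy visits. The safety figures may look less favourable. No dose or treatment rule changes.

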#### 5.2 Aim of Study

In a previous pilot study conducted by our group, we investigated the use of IV iron without ESAs in a group of non-iron deficient anemic cancer patients undergoing chemotherapy. Patients were given 12 weekly short infusions of ferric sucrose while on chemotherapy. The mean increment in hemoglobin level for the 15 patients who completed at least 9 treatments was 1.7 g/dL (median, 1.1 g/dL; range, -1.9 g/dL to 3.2 g/dL). Five (20.0%) patients were transfused and considered as treatment failures. No treatment-related adverse events were reported.

With such results and to move forward with the investigation, we have considered using a new intravenous iron formulation. Ferric carboxymaltose (FCM), is widely used to treat iron deficiency anemia in different clinical settings including pregnancy-related and in chronic renal failure patients..

Therefore, the study aims to investigate the effect of FCM without ESAs on anemic cancer patients undergoing chemotherapy or radiotherapy; stratified by status of iron deficiency (i.e. non-iron deficient vs. iron deficient patients).

Furthermore, we aim to investigate the value of Hepcidin and also CRP (which is closely associated with inflammatory cytokines, as well) as predictors of response.

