#### **6.3 Study Endpoints**

#### **6.3.1 Primary Endpoint:**

- Response Rate: Percentage of patients with Hb increment of at least 1.0 gm/dL.
- Proportion of patients achieving correction of anemia (Hb >11.0 gm/dL)
- The mean Hb change from baseline to week 12

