#### **6.3.2 Secondary Endpoints:**

- Response in relation to Hepcidin level.
- Response in relation to CRP level.
- Response in relation to base line iron deficiency status; iron-deficient or not.
- Parentage of patients who will require blood transfusion or ESA treatment

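### Read literally, the treatment-failure rule in 8.3 omits transfusion or ESA given for the study anemia, so rescued patients can count as Hb responders, and named failures may be replaced

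*Protocol*

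**What the plan says.** Protocol 8.3 says a "patient will be dropped out and will be considered treatment failure if" either of two things happens. The first is "Receive ESA or blood transfusion for medical reasons not related to the study". The second is "if they Develop a grade IV toxicity of any kind in the week between the initial and the remaining dose", where this is possibly related to the study drug. The paragraph just above says: "Withdrawn subjects will be replaced to have a complete set of 50 analyzable subjects in each strata".

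Protocol 6.3.1 places three measures under the primary endpoint: "Response Rate: Percentage of patients with Hb increment of at least 1.0 gm/dL"; "Proportion of patients achieving correction of anemia (Hb >11.0 gm/dL"); and the mean Hb change to week 12. None is conditional on being free of transfusion or ESA, and the first two carry no time point.

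Transfusion and ESA use appears as a secondary endpoint in 6.3.2 ("Parentage of patients who will require blood transfusion or ESA") and as counts and percentages under safety in 13.3 and the SAP. The efficacy analyses in 13.2 and the SAP mention neither treatment failure nor rescue.

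On the group's own pilot, 5.2 reports: "Five (20.0%) patients were transfused and considered as treatment failures".

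**The concern.** Needing a transfusion or ESA because the anemia under study did not improve is the plainest failure of the treatment. On its literal wording, the rule covers only rescue given for unrelated reasons and is silent on this case.

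The silence matters because rescue raises the variable being measured. Section 5.1.1 describes transfusion as quickly effective in restoring Hb, and 5.1.2 says ESAs raise Hb significantly. Hb is read at weeks 3, 6, 9 and 12, so a visit soon after rescue could supply the required increment. The design is single-arm and open-label, so no control group carries the same distortion. The bias runs towards FCM, on the primary endpoint, in both strata.

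There is a second route to the same bias. Patients who do meet the rule are both failures and drop-outs, and withdrawn subjects are replaced until 50 are analyzable. The text does not say whether a dropped failure is among the analyzable 50.

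**Working it through.** **1. Is the gap closed elsewhere?**

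| Place | What it adds |
|---|---|
| 8.3, second ground | Toxicity between doses only; nothing on rescue |
| 6.3.1 | Hb increment, Hb level, mean change; no rescue condition |
| 13.2 and SAP analysis section | Paired t-tests, univariate tests, logistic regression; no failure rule |
| 6.3.2, 13.3 and SAP safety section | Rescue is counted, but not linked to response |
| 5.2 (pilot) | Transfused patients counted as failures, without qualification |

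No place says how a patient rescued for the study anemia enters the response analysis.

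**2. Inputs for the size.**
- Stratum size n = 50 (8.1, 13.1). I take it as stated; its derivation is a separate matter and does not affect this point.
- Transfused share t. The pilot's five patients at 20.0% imply 5 / 0.20 = 25 patients. I use t = 20% and, as a lower case, t = 10%. Both are assumptions for this trial.
- Share q of those patients who then meet the Hb threshold. The documents give no value, so I use 25%, 50% and 100%.
- All these transfusions are assumed to be for the study anemia.

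**3. Inflation of the response rate**, compared with counting every rescued patient as a non-responder: t × q.

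| t | Patients of 50 | q = 25% | q = 50% | q = 100% |
|---|---|---|---|---|
| 20% | 10 | 5 points | 10 points | 20 points |
| 10% | 5 | 2.5 points | 5 points | 10 points |

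A rate reported as 54% under the literal rule (27/50) would be 49%, 44% or 34% at t = 20%, and 51.5%, 49% or 44% at t = 10%. At the extreme, 27/50 has an exact 95% interval of 39.3% to 68.2%; 17/50 has 21.2% to 48.8%.

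**4. Effect on a comparison with 50%.** Section 13.1 speaks of superiority and treats 50% as the clinically meaningful rate, but 13.2 and the SAP list no test against it. As an illustration only, an exact one-sided 5% rule with n = 50 needs at least 32 responders. Suppose the true rate, with rescue counted as failure, is exactly 50%. Then P(X ≥ 32) is:
- no inflation (p = 0.50): 0.032
- 5 points (p = 0.55): 0.127
- 10 points (p = 0.60): 0.336
- 20 points (p = 0.70): 0.859

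**5. The denominator route.** Take 50 enrolled, 10 of them named failures, and 17 responders among the other 40. Kept in, the rate is 17/50 = 34%. If the 10 are replaced by patients who respond like the other 40, the expected rate is 17/40 = 42.5%, which is 8.5 points higher. The counts are again assumed.

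**The case against.** The strongest reply is that the clause was meant differently: a transfusion or ESA given for clinical need rather than required by the study. No study procedure calls for either, so on that reading every clinically indicated rescue is a failure. This fits the pilot's handling, and the narrow reading would fail patients with unrelated transfusions while sparing the true failures, which is unlikely to be intended. The argument stands as far as it goes: a reader might infer that the protocol declares rescued patients not to be failures, and the text does not establish that. But neither reading is stated, so two analysts could reach different primary results from the same data. The wider reading also leaves the denominator question open.

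Other stronger inferences fail too:
- A single rescued patient cannot satisfy all three primary measures. The third is a group mean, which such a patient can only shift.
- Twenty points is a ceiling, not an expectation. Section 5.1.1 calls the effect of transfusion temporary. If the increment is taken from baseline, a patient whose Hb fell before rescue must regain that fall plus 1.0 g/dL.
- The 20% comes from non-iron-deficient patients given weekly ferric sucrose. Applying it to FCM, and to the iron-deficient stratum, is an assumption.
- One cannot say that the 0.54 planning rate was defined differently. No whole count out of 25 gives it (13/25 = 0.52, 14/25 = 0.56), nor does 8/15 = 0.53 among the completers. Its denominator, and its handling of transfused patients, are unknown.
- Moving a point estimate across 50% is not a false claim of superiority. At 27/50 the interval includes 50%, and the exact one-sided p is 0.34.

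Finally, rescue is reported separately, so readers would see how many patients are affected. That limits concealment but does not repair the responder definition.

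**Conclusion.** The point holds as an ambiguity with a one-directional consequence. On the literal wording, rescue for the study anemia is not a named failure, and nothing in the endpoints or the SAP keeps Hb measured after rescue from counting as response or correction or from raising the mean change. Named failures may also be replaced out of the denominator.

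Under the assumptions in the working, the response rate is inflated by 5 to 20 points if 20% are transfused and by 2.5 to 10 points if 10% are. The direction follows from the text; the size rests on t and q, which the documents do not give for this trial. Because it bears on the primary endpoint of an uncontrolled trial, this is more than missing detail.

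**What to change.** State one rule, for analysis only, in 8.3, 6.3.1 and the SAP:

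- Any patient given a transfusion or ESA for any reason between the first infusion and week 12 is a non-responder for both response and correction, stays in the denominator and is not replaced.
- Hb measured after the rescue is not used as a response value.
- For the mean change, state one rule. For example, analyse Hb up to the rescue, with a sensitivity analysis using all observed Hb.

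This follows the pilot's handling of transfused patients and removes the need to judge whether a rescue was related to the study. Patient care is unchanged. The cost is a short text change in three places and a reported response rate that may be lower.

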#### 8.2.2 Exclusion Criteria

Patient has Hb ≤ 8.0 g/dL

- Patient presenting with hematologic malignancy including any of the following: Acute Leukemia, MDS, CML, CLL, Multiple Myeloma, Myelodysplastic syndrome and lymphoma with bone marrow involvement
- Prior gastric surgery.
- Patients on definitive radiotherapy alone.
- Patients with relevant history (within six weeks) or clinical evidence of hemolysis or active bleeding that could, in the investigator's judgment, be a potential cause for the anemia (no gross hematuria, hemoptysis, hematochezia or melena and negative stool for hemoccult-at least one reading)
- Presence of other nutritional anemia; deficiency of vitamin B12 <187 pg/ml and deficiency of Folate < 3.1 ng/ml according to the local laboratory normal ranges

- Patient has Iron overload (Serum Ferritin > 800 ng/ml or Transferrin saturation (TSAT) > 40%)
- Patient is pregnant or lactating.
- Patient has a personal or family history of hemochromatosis.
- Patient has hypersensitivity to any form of IV iron.
- Patient has received red blood cells (RBCs) transfusion or used erythropoietin within 2 weeks of enrollment into the study.
- Patient has received any form of IV iron within the last 12 weeks
- Patient has received oral iron supplements within 1 month of enrollment to the study, except for multivitamin supplements containing less than 30mg iron.

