#### 9.4 Stopping Rules

There are no formal stopping rules for the study but should the patient develop anaphylaxis or para-venous leak is observed, the infusion will be interrupted and patient treatment will be left to the attending physician.

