#### **10.2 Treatment phase**

[figure not shown]
- Patients will receive their prescribed FCM infusion in the KHCC infusion areas or in the inpatients units.
- FCM will be administered as a single infusion if the needed dose is 1000 mg as a short IV infusion, diluted in 250mL of 0.9 saline over 15-30 minutes.

- If the needed FCM dose is > 1000 mg, an initial dose of 1000 mg will be given as above and the remaining dose will be given the week after in a similar fashion if the remaining dose is 1000mg; if the remaining dose is 500mg, then it will be given as a short IV infusion, diluted in 100mL of 0.9 saline over a minimum period of 6 minutes.
- During the infusion, the patient will be monitored for adverse events.

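### A drug reaction at the first infusion can be counted as a failure, replaced, or judged on Hb after a partial dose, because only grade IV toxicity mandates drop-out

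*Protocol*

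**What the plan says.** Four parts of the protocol bear on a patient who reacts at the first infusion.

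- **Section 8.3, mandatory drop-out.** Two events make a patient a drop-out and a treatment failure. One is to "Receive ESA or blood transfusion for medical reasons not related to the study". The other applies "if they Develop a grade IV toxicity of any kind in the week between the initial and the remaining dose", provided that a link to the study drug is possible.
- **Section 8.3, discretionary removal.** "The investigator may remove a patient from the study if, at his discretion, the participation is seen to jeopardize the patient safety". No grade is attached. Patients may also leave at will. Withdrawn patients are replaced until each stratum has 50 who can be analysed.
- **Section 9.4.** For anaphylaxis or a para-venous leak, "the infusion will be interrupted and patient treatment will be left to the attending physician". The section does not mention the remaining dose or whether the patient stays in the study.
- **Section 10.2.** When more than 1000 mg is needed, "an initial dose of 1000 mg will be given as above and the remaining dose will be given the week after". No condition on how the first infusion was tolerated is attached.

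The SAP and protocol section 13.2 say nothing about treatment failures, replaced patients or the denominator of the response rate.

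**The concern.** Grade IV is the only toxicity for which the protocol fixes both what happens to the patient and how the patient is counted. Below that grade, both depend on which section is applied. Investigator removal leads to withdrawal and replacement, so the patient leaves the denominator. An interruption under section 9.4 with no removal leaves the patient in the study, to be judged on Hb after what may be a partial dose.

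The response rate in each stratum is the first-listed primary endpoint. Replacing a patient who was taken off because of the drug swaps a likely non-responder for someone with an ordinary chance of responding. That moves the rate in one direction, upward. A reader of the final report could not tell how many patients took each route unless it is reported.

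**Working it through.** The plan states no figure on this point, so there is none to reproduce. The check is a comparison of the rules, followed by a calculation of scale.

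**Step 1: the routes side by side**

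| Reaction at infusion 1, possibly drug-related | Rule | Status in the response rate |
|---|---|---|
| Grade IV, before the remaining dose | 8.3, mandatory drop-out | Treatment failure |
| Below grade IV, investigator removes the patient | 8.3, discretion | Withdrawn and replaced; not counted |
| Infusion interrupted, patient not removed | 9.4 | Not stated; by default judged on Hb, possibly after a partial dose |
| Below grade IV, patient not removed | 10.2 | Remaining dose as scheduled; judged on Hb |

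**Step 2: effect of one replaced patient.** Inputs: 50 per stratum and a planning response proportion of 0.54 (both from section 13.1). Let r be the number of responders among the other 49 patients.

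- Kept as a failure: r/50.
- Replaced by a patient who responds with probability 0.54: expected rate (r + 0.54)/50.
- Expected difference: 0.54/50 = 1.08 percentage points.
- Largest difference, if the replacement responds: 1/50 = 2 percentage points.

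For scale, section 13.1 sets 0.54 against a clinically meaningful rate of 0.50. In 50 patients that is 27 against 25 responders, a gap of two patients.

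**Step 3: how often it could arise.** Input: the adverse reaction table in section 9.1 lists hypersensitivity as uncommon, 0.1% to below 1%. Expected cases are n × p, and the chance of at least one is 1 − (1 − p)^n.

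| n | p | Expected cases | Chance of at least one |
|---|---|---|---|
| 100 | 0.001 | 0.1 | 9.5% |
| 100 | 0.01 | 1.0 | 63.4% |
| 50 | 0.001 | 0.05 | 4.9% |
| 50 | 0.01 | 0.5 | 39.5% |

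These are upper bounds for hypersensitivity. A remaining dose exists only for patients who need more than 1000 mg. Three of the four dose cells do (1500, 1500 and 2000 mg), but cells are not patients, and the documents give no distribution across them. The reaction must also occur at the first infusion and be below grade IV.

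**Step 4: expected shift per stratum.** Suppose every hypersensitivity case were removed and replaced. The expected upward shift is 0.05 × 1.08 = 0.05 to 0.5 × 1.08 = 0.54 percentage points. If every replacement responded, it is 0.05 × 2 = 0.1 to 0.5 × 2 = 1.0 percentage points.

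The same table lists urticaria, pruritus and rash separately as uncommon. They are not in these counts and would add to them if they led to removal.

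**The case against.** The best defence is that the protocol does not leave a reacting patient unprotected. Section 8.3 lets the investigator remove a patient for safety at any grade, section 11.2 foresees discontinuation because of an adverse event with no grade limit, and section 9.4 interrupts the infusion for anaphylaxis. Discretion that depends on grade is a legitimate design choice. All of that stands. It also rules out three stronger readings that a reader might infer:

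- **That only a grade IV event removes a patient.** It is the only toxicity that mandates drop-out; others may lead to removal at discretion.
- **That the entry exclusion conflicts with the second infusion.** Section 8.2.2 bars entry if "Patient has hypersensitivity to any form of IV iron", and a patient who reacts at the first infusion might seem to meet it. But the same list excludes anyone given IV iron in the preceding 12 weeks. Re-applied between infusions, it would exclude every two-dose patient. The list governs enrolment.
- **That the safety count depends on the route taken.** Sections 11 and 11.3 call for all adverse events to be recorded with intensity, outcome and relationship to the product, and section 13.3 reports their rate and incidence. None of this turns on grade or on how the patient left.

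It can also be said that replacing withdrawn patients affects every kind of withdrawal, not just this one. That is true. The case is sharper here because the protocol already counts the grade IV form of the same event as a failure. Discretion settles how the patient is managed; it does not settle how the patient is counted.

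**Conclusion.** The concern holds as a gap in the rules and an inconsistency in counting. It does not show that the protocol obliges re-dosing after a reaction: section 10.2 sets a schedule and does not override the discretion in section 8.3. What is missing is a stated consequence, for the remaining dose and for study status, of a reaction below grade IV or an interrupted first infusion. Without it, similar drug reactions enter the response rate differently, and the replacement route favours the treatment.

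The size is modest: up to 2 percentage points per replaced patient, and an expected shift of at most about 1 point per stratum from hypersensitivity. This rests on three assumptions: that the protocol's frequency band applies to these patients, that the 0.54 planning rate describes replacements, and that a removed patient would otherwise be counted as a failure, as a grade IV case is. The 63.4% is a ceiling, not a forecast. The change is worth making because it is cheap and removes a bias of known direction, not because it is likely to alter the conclusion.

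**What to change.** 1. **Reconcile protocol sections 8.3, 9.4 and 10.2** so that a reaction or an interrupted infusion at the first dose has a stated consequence for the remaining dose and for study status. Which clinical rule applies is for the investigator to decide; it may depend on grade.
2. **Fix the counting in section 13.2 and the SAP.** For the response rate, do not replace patients removed for a reaction possibly related to the study drug. Keep them in the denominator as treatment failures, as grade IV cases already are, whatever the grade or route of removal.
3. **Report the dose actually infused** and the number of patients who took each route. The CRF is not among the documents, so it should be checked that it captures the infused dose; if not, one field is needed.

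The cost is a few sentences and at most one CRF field. The downside is a slightly less favourable response rate, by up to 2 percentage points per affected patient in a stratum of 50.
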